3.2. Discussion of Study Design

The fixed sequence design used in this study is typical for interaction studies where a relatively small number of subjects are required. This study will be open-label because the study endpoints are not considered subjective.

Omeprazole is a well-established PPI and has been used in clinical drug interaction studies.

The proposed regimen for omeprazole in this study is to take omeprazole alone QD for 5 days followed by coadministration of omeprazole and sotorasib plus an acidic beverage. An acidic beverage is expected to temporarily lower gastric pH. The 5-day lead-in period is to maximize the antisecretory effect because the inhibition of acid secretion increases with repeated QD dosing, reaching a plateau after 4 days. 12

Conducting the study in healthy subjects mitigates the potential confounding effects of the disease state and concomitant medications.

18 May 2022 Page 20 of 69

3.3. Selection of Doses in the Study

The approved dose level of sotorasib is 960 mg.¹⁴ There have been 6 clinical studies in healthy subjects where sotorasib has been administered at dose levels up to 960 mg and was well tolerated across the studies. In addition, there have been no dose-limiting toxicities observed with sotorasib monotherapy at 960 mg in subjects with advanced tumors with the *KRAS p.G612C* mutation. Please refer to the IB¹ for more information.

In this study, the 40 mg omeprazole dose will be administered orally. This is a clinically recommended dose level and a dose level used to evaluate clinical drug interactions.

4. SELECTION OF STUDY POPULATION

4.1. Inclusion Criteria

Subjects must satisfy all of the following criteria prior to enrollment unless otherwise stated:

- 1. Subject has provided informed consent before initiation of any study-specific activities/procedures.
- 2. Healthy male or nonchildbearing female subjects, between 18 and 60 years of age (inclusive) at the time of Screening.
- 3. In good health, determined by no clinically significant findings from medical history, physical examination, 12-lead ECGs, vital signs measurements, and clinical laboratory evaluations (congenital nonhemolytic hyperbilirubinemia [eg, suspicion of Gilbert's syndrome based on total and direct bilirubin] is not acceptable) as assessed by the Investigator (or designee).
- 4. Body mass index between 18 and 30 kg/m² (inclusive) at the time of Screening.
- 5. Females must be of nonchildbearing potential, defined as permanently sterile (ie, due to hysterectomy, bilateral salpingectomy, or bilateral oophorectomy) or postmenopausal (defined as at least 45 years of age with amenorrhea for 12 months without an alternative medical cause and follicle-stimulating hormone [FSH] level ≥ 40 mIU/mL).

4.2. Exclusion Criteria

Subjects will be excluded from the study if they satisfy any of the following criteria prior to enrollment unless otherwise stated:

1. History or evidence, at Screening or Check-in, of clinically significant disorder, condition, or disease not otherwise excluded that, in the opinion of the Investigator (or designee), would pose a risk to subject safety or interfere with the study evaluation, procedures, or completion.

18 May 2022 Page 21 of 69

- 2. History or evidence of clinically significant arrhythmia at Screening, including any clinically significant findings on the ECG taken at Check-in.
- 3. A QT interval corrected for heart rate (HR) based on the Fridericia correction (QTcF) interval > 450 msec in male subjects or > 470 msec in female subjects or history/evidence of long QT syndrome; and/or PR interval > 200 msec, second degree atrioventricular (AV) block or third degree AV block, at Screening or Check-in. Electrocardiograms will be taken as single ECGs. If parameters are out-of-range, the site will collect 2 more ECGs and then calculate the mean to determine eligibility.
- 4. Systolic blood pressure > 140 mmHg or < 90 mmHg, or diastolic blood pressure > 90 mmHg, or HR > 100 bpm, at Screening or Check-in. Subjects with out-of-range values that are not clinically significant (as determined by the Investigator) may have the test repeated once during Screening or Check-in (within 1 hour of original assessment) and the subject may be enrolled if a repeated value is within normal range.
- 5. History suggestive of achlorhydria, esophageal (including esophageal spasm, esophagitis), gastric, or duodenal ulceration or bowel disease (including, but not limited to, peptic ulceration, gastrointestinal bleeding, ulcerative colitis, Crohn's disease, or irritable bowel syndrome), or a history of gastrointestinal surgery other than uncomplicated appendectomy.
- 6. Inability to swallow oral medication or history of malabsorption syndrome.
- 7. History of hypersensitivity, intolerance, or allergy to any drug compound, food, or other substance, unless approved by the Investigator (or designee) and in consultation with the Sponsor.
- 8. Poor peripheral venous access.
- 9. Estimated glomerular filtration rate less than 70 mL/min/1.73 m² as calculated by the CKD-EPI Creatinine Equation¹⁸, at Screening or Check-in. Subjects with out-of-range values may have the test repeated once at the discretion of the Investigator.
- 10. ALT or AST should be ≤ULN at Screening or Check-in (for these parameters, a subject with out-of-range values may have the tests repeated once and the subject may be enrolled if the repeated values are ≤ULN or if the repeated values above ULN are deemed not clinically significant by the Investigator [eg, 1.5 x ULN]).
- 11. Positive hepatitis B or hepatitis C panel and/or positive human immunodeficiency virus test at Screening. Subjects whose results are compatible with prior immunity (vaccination or prior infection) may be included.
- 12. Use of any over-the-counter or prescription medications within 30 days or 5 half-lives (whichever is longer) before enrollment, unless deemed acceptable by the Investigator (or designee) and in consultation with the Sponsor.
 - a. Acetaminophen [paracetamol] (up to 2 g per day) for analgesia will be allowed.

18 May 2022 Page 22 of 69

- 13. All herbal medicines (eg, St. John's wort), vitamins, and supplements consumed by the subject within the 30 days prior to enrollment, unless deemed acceptable by the Investigator (or designee) and in consultation with the Sponsor.
- 14. Consumption of foods and beverages containing poppy seeds, grapefruit, or Seville oranges within 7 days prior to Check-in.
- 15. History of alcoholism or drug/chemical abuse within 1 year prior to Check-in.
- 16. Alcohol consumption from 48 hours prior to Check-in.
- 17. Regular alcohol consumption of > 14 units per week for males and > 7 units per week for females. One unit of alcohol equals 12 oz (360 mL) beer, 1½ oz (45 mL) liquor, or 5 oz (150 mL) wine.
- 18. Use of tobacco- or nicotine-containing products within 6 months prior to Check-in.
- 19. Positive test for illicit drugs, cotinine (tobacco or nicotine use) at Screening or Check-in and/or alcohol use at Check-in only.
- 20. Consumption of caffeine-containing foods and beverages within 48 hours prior to Check-in.
- 21. Female subjects with a positive pregnancy test at Screening or Check-in.
- 22. Female subjects lactating/breastfeeding or who plan to breastfeed during the study through 7 days after the EOS.
- 23. Unwilling to adhere to contraceptive requirements through 7 days after the EOS (see).
- 24. Unwilling to abstain from sperm donation through 7 days after the EOS (see).
- 25. Male subjects with a female partner of childbearing potential and not willing to inform his partner of his participation in this clinical study.
- 26. Male subjects with a pregnant partner or partner planning to become pregnant who are unwilling to practice abstinence (refrain from heterosexual intercourse) or use contraception while the subject is on study through 7 days after the EOS.
- 27. Subject has received a dose of an investigational drug within the past 30 days or 5 half-lives, whichever is longer, prior to Check-in.
- 28. Have previously completed or withdrawn from this study or any other study investigating sotorasib or have previously received the investigational product.
- 29. Donation of blood from 90 days prior to Check-in, plasma from 2 weeks prior to Check-in, or platelets from 6 weeks prior to Check-in.
- 30. Receipt of blood products within 2 months prior to Check-in.
- 31. Unwilling to abide with study restrictions.
- 32. Subjects who, in the opinion of the Investigator (or designee), should not participate in this study.

18 May 2022 Page 23 of 69

33. Performed strenuous exercise, began a new exercise program, or participated in any unusually strenuous physical exertion within 7 days prior to Check-in.

4.3. Screen Failures and Rescreening

Screen failures are defined as subjects who consent to participate in the clinical study but are not subsequently enrolled in the study because they do not meet eligibility requirements. A minimal set of screen failure information will be collected that includes demography, screen failure details, eligibility criteria, medical history, prior therapies, and any serious adverse events.

Individuals who do not meet the criteria for participation in this study (screen failure) may be rescreened only once.

4.4. Subject Number and Identification

Subjects will have a unique identification number used at Screening. Subjects will be assigned a subject number prior to the first dosing occasion. Assignment of subject numbers will be in ascending order and no numbers will be omitted (eg, Subjects 0101, 0102, 0103). Replacement subjects will be assigned a subject number corresponding to the number of the subject he/she is replacing plus 1000 (eg, Subject 1101 replaces Subject 0101).

Subjects will be identified by subject number only on all study documentation. A list identifying the subjects by subject number will be kept in the Site Master File.

4.5. Subject Withdrawal and Replacement

A subject is free to withdraw from the study at any time. In addition, a subject will be withdrawn from dosing if any of the following criteria are met:

- change in compliance with any inclusion/exclusion criterion that is clinically relevant and affects subject safety as determined by the Investigator (or designee)
- noncompliance with the study restrictions that might affect subject safety or study assessments/objectives, as considered applicable by the Investigator (or designee)
- occurrence of any Common Terminology Criteria for Adverse Events (CTCAE) v5.0
 Grade ≥3 adverse event
- occurrence of Grade 2 adverse event considered by the Investigator (or designee) to be at least possibly related to sotorasib and, in the opinion of the Investigator (or designee), warrants subject withdrawal (eg, neuropathy, chronic diarrhea, etc)
- any clinically relevant sign or symptom that, in the opinion of the Investigator (or designee), warrants subject withdrawal.

If 2 or more subjects are withdrawn from the study due to adverse events that are considered by the Investigator to be at least possibly related to sotorasib or if there is 1 Grade 3 event, dosing

18 May 2022 Page 24 of 69

will be paused, and the Investigator and Sponsor will convene to review the data and determine the next step.

If a subject is withdrawn from dosing, the Sponsor (or designee) will be notified and the date and reason(s) for the withdrawal will be documented in the subject's electronic Case Report Form (eCRF). If a subject is withdrawn, efforts will be made to perform all EOS assessments, if possible (Appendix 8). Other procedures may be performed at the Investigator's (or designee's) and/or Sponsor's discretion. If the subject is in-house, these procedures should be performed before the subject is discharged from the clinic. The Investigator (or designee) may also request that the subject return for an additional follow-up visit. All withdrawn subjects will be followed until resolution of all their adverse events, or until the unresolved adverse events are judged by the Investigator (or designee) to have stabilized.

Subjects who are withdrawn for reasons not related to study drug may be replaced following discussion between the Investigator and the Sponsor. Subjects withdrawn as a result of adverse events/serious adverse events thought to be related to the study drug will generally not be replaced.

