4.7. Discontinuation of Study Treatment

Subjects (or a legally acceptable representative) can decline to continue receiving investigational product and/or other protocol-required therapies or study procedures at any time during the study but continue participation in the study. If this occurs, the Investigator is to discuss with the subject the appropriate processes for discontinuation from investigational product or other protocol-required therapies and must discuss with the subject the possibilities for continuation of the Schedule of Assessments (Appendix 8) including different options of follow-up (eg, in person, by phone/mail, through family/friends, in correspondence/communication with other treating physicians, from the review of medical records) and collection of data, including endpoints, adverse events, serious adverse events, and must document this decision in the subject's medical records. Subjects who have discontinued investigational product and/or other protocol-required therapies or study procedures should not be automatically removed from the

18 May 2022 Page 25 of 69

study. Whenever safe and feasible, it is imperative that subjects remain on study to ensure safety surveillance and/or collection of outcome data.

Reasons for removal from protocol-required investigational product(s) or procedural assessments include any of the following:

- Decision by the Sponsor
- Lost to follow-up
- Death
- Protocol deviation
- Noncompliance
- Adverse events
- Subject request
- Pregnancy.

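### Protocol Section 4.5 takes subjects off dosing for adverse events, but its two-subject pause rule counts only those who leave the study

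*Protocol*

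**What the plan says.** Protocol Section 4.5 opens with two different states. The first is leaving the study: "A subject is free to withdraw from the study at any time". The second is introduced as an addition to it: "a subject will be withdrawn from dosing if any of the following criteria are met". Five criteria follow, and all lead to the second state. One of them is a Grade 2 event, at least possibly related to sotorasib, that in the Investigator's opinion "warrants subject withdrawal (eg, neuropathy, chronic diarrhea, etc").

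The study-level rule comes next and has two limbs. The count limb reads "If 2 or more subjects are withdrawn from the study due to adverse events that are considered by the Investigator", the condition being a link to sotorasib judged possible or stronger. The severity limb needs a single Grade 3 event and no withdrawal. If either is met, dosing is paused while the Investigator and Sponsor review the data.

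The rest of the section mixes its terms: "If a subject is withdrawn from dosing, the Sponsor (or designee) will be notified", then "If a subject is withdrawn, efforts will be made to perform all EOS assessments, if possible (Appendix 8"), then "All withdrawn subjects will be followed until resolution of all their adverse events", or until those events are judged stable.

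Section 4.7 says: "Subjects who have discontinued investigational product and/or other protocol-required therapies or study procedures should not be automatically removed from the" study. It adds that they should remain on study whenever that is safe and feasible, and it lists adverse events among the reasons for removal from product.

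**The concern.** The individual rule produces one state and the study-level rule counts another. Nothing in the protocol says that withdrawal from dosing counts as withdrawal from the study for the purpose of the pause. A site that follows Section 4.7 could stop a subject's dosing for a related event, keep the subject on study for follow-up, and so leave the pause count unchanged.

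The severity limb already deals with Grade 3 events, so the count limb does independent work only for related events below Grade 3. It is the only numeric study-level trigger for such events. If it depends on which state the site records, other subjects could go on to the second 960 mg sotorasib dose on Day 9 without the review that the rule appears designed to force. These are healthy volunteers who, by Section 1.4.1.1, gain no health benefit beyond an assessment of their medical status.

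**Working it through.** **1. Comparison of wording**

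| Rule | State it produces or counts | Where |
|---|---|---|
| Five individual criteria | Withdrawn from dosing | Section 4.5 |
| Pause, count limb | Withdrawn from the study, related event, at least 2 subjects | Section 4.5 |
| Pause, severity limb | 1 Grade 3 event | Section 4.5 |
| Default after stopping product | Stay on study where safe and feasible | Section 4.7 |

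Other parts of the protocol also keep the states apart. Section 8.4 tabulates events leading to withdrawal from product or other required therapies. The notification forms in Appendix 5 ask separately whether product was stopped and whether the subject left the study. Appendix 7 requires at least 4 weeks of close observation after product is discontinued for liver findings.

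**2. A count that needs no event rate**

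Take exactly two subjects withdrawn from dosing for related events below Grade 3. Let k be the number of them also recorded as leaving the study.

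| k | Literal count | Literal rule pauses? | Count if dosing withdrawals are included | Pauses? |
|---|---|---|---|---|
| 0 | 0 | No | 2 | Yes |
| 1 | 1 | No | 2 | Yes |
| 2 | 2 | Yes | 2 | Yes |

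**3. Illustrative probabilities**

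The plan has no figure to reproduce: the documents give no event rate, and Section 8.1 states that the sample size does not rest on power calculations. Inputs:

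- n = 14, the maximum enrolment in Section 3.1.
- p, the chance that a subject is withdrawn from dosing for a related event below Grade 3 between the Day 1 and Day 9 doses. This is assumed.
- s, the share of those subjects also recorded as leaving the study. This is assumed.
- Subjects are taken as independent.

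The chance that the count limb fires, with r = p × s, is

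P(at least 2) = 1 − (1 − r)^14 − 14 r (1 − r)^13.

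Worked case, p = 5% and s = 1: 1 − 0.4877 − 14 × 0.05 × 0.5133 = 1 − 0.4877 − 0.3593 = 0.153.

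| p | s = 1 (same as counting dosing withdrawals) | s = 0.5 | s = 0 |
|---|---|---|---|
| 1% | 0.8% | 0.2% | 0% |
| 2% | 3.1% | 0.8% | 0% |
| 5% | 15.3% | 4.7% | 0% |

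The shortfall from the literal wording is the first column minus the relevant one. At s = 0.5 it is 0.6, 2.3 and 10.6 points. At s = 0 it is 0.8, 3.1 and 15.3 points. At s = 1 it is zero.

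**The case against.** The strongest reply is that Section 4.5, read as a whole, means one thing by withdrawal. Two of the criteria for stopping dosing are themselves phrased as warranting subject withdrawal. The text slides from withdrawn from dosing to plain withdrawn without marking a change. It sends those subjects to end-of-study assessments, done before discharge if they are in-house, and then to adverse event follow-up and possible replacement. That looks like leaving the study. Section 4.7 opens with subjects who choose to stop product, and its preference for retention is qualified by safety and feasibility.

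This makes the inclusive reading plausible, and follow-up alone does not separate the two states. It does not settle the count. No sentence equates the states for the pause rule, and Section 4.7's retention language covers discontinued subjects generally, with adverse events among the listed reasons.

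The second reply is that little is at stake. There is one site and at most 14 subjects. The Sponsor is told of every withdrawal from dosing and can stop the study under Section 4.6. One Grade 3 event pauses dosing, and liver findings have their own withholding rules in Appendix 7. Below Grade 3, relatedness and the need to withdraw are themselves matters of judgement. All of this is correct and limits the exposure. But notification and the power to stop the study do not themselves pause dosing, whereas the count limb is meant to do so once its conditions are met.

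The third reply, that the probabilities rest on assumed inputs, is also correct. They show scale only.

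**Conclusion.** The concern holds. On the literal text, two subjects taken off dosing for related events below Grade 3 who stay on study count as 0, and no pause is mandated. That conclusion rests on the wording alone. How often it would matter is unknown: under the assumptions above, the loss in the chance of a pause runs from zero, if every such subject leaves the study, to 0.8, 3.1 or 15.3 points at p = 1%, 2% or 5%, if all stay.

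Day 9 sotorasib is the main dose at stake but not the only one. A pause would also affect omeprazole on Days 4 to 8 and, if enrolment is staggered, later subjects' Day 1 dose. This is a defect in the wording of a safety rule and does not touch the PK analysis. It should be corrected. Confidence is medium, because the inclusive reading may be what was intended.

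**What to change.** In the pause sentence of Section 4.5, replace *withdrawn from the study* with *withdrawn from dosing or from the study*. Leave the threshold of two subjects, the relatedness condition and the single Grade 3 event as they are.

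The cost is one phrase in a protocol amendment, which under Appendix 6 needs IRB approval before it takes effect. There may be more pause reviews; under the illustrative assumptions the increase equals the shortfall shown above, so at most 0.8, 3.1 or 15.3 points. If the inclusive reading was always intended, the rewording changes nothing in practice and removes the doubt. Sample size, visits and the PK analysis stay the same.

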3. INVESTIGATIONAL PLAN

3.1. Overall Study Design and Plan

[figure not shown]
This will be a Phase 1, single-center (United States), open-label, fixed sequence study to investigate the effect of coadministration of omeprazole with an acidic beverage on the PK of sotorasib in healthy male and healthy female subjects. Up to 14 subjects will be enrolled to ensure that 12 subjects complete the study. All subjects will receive each of the following treatments:

- Day 1: 960 mg sotorasib (8 x 120 mg tablets) administered orally with 240 mL of water after an overnight fast of at least 10 hours
- Days 4 to 8: 40 mg omeprazole (delayed release capsule) administered orally with 240 mL of water QD after an overnight fast of at least 10 hours
- Day 9: 40 mg omeprazole (delayed release capsule) followed by 960 mg sotorasib (8 x 120 mg tablets) administered orally within 5 minutes with 240 mL of an acidic beverageafter an overnight fast of at least 10 hours.

An overview of the study design is shown in Figure 1.

18 May 2022 Page 19 of 69

Figure 1: Study Schematic

Potential subjects will be screened to assess their eligibility to enter the study within 28 days prior to the first dose administration. Subjects will be admitted into the Clinical Research Unit (CRU) on Day -1 and be confined to the CRU until discharge/end of study (EOS) on Day 11.

The total duration of study participation for each subject (from Screening through EOS visit) is anticipated to be approximately 5.5 weeks.

The start of the study is defined as the date the first enrolled subject signs an Informed Consent Form (ICF). The point of enrollment occurs at the time of subject number allocation. The end of the study is defined as the date of the last subject's last assessment (scheduled or unscheduled).

A Schedule of Assessments is presented in Appendix 8.

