4.6. Study Termination

The Sponsor may stop the study or study site participation in the study for medical, safety, regulatory, administrative, or other reasons consistent with applicable laws, regulations, and Good Clinical Practice. Both the Sponsor and the Investigator reserve the right to terminate the Investigator's participation in the study according to the Clinical Trial Agreement. The Investigator is to notify the Institutional Review Board (IRB) in writing of the study's completion or early termination and send a copy of the notification to the Sponsor. The Sponsor reserves the unilateral right, at its sole discretion, to determine whether to supply investigational product and by what mechanism, after termination of the study.

In addition, the study may be terminated by the Sponsor at any time and for any reason. If the Sponsor decides to terminate the study, they will inform the Investigator as soon as possible.

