All serious adverse events will be collected, recorded, and reported to the Sponsor within 24 hours of the Investigator's awareness of the event. The Investigator will submit any updated serious adverse event data to the Sponsor within 24 hours of it being available.

Since the criteria for the CTCAE grading scale differs from the regulatory criteria for serious adverse events, if adverse events correspond to Grade 4 CTCAE toxicity grading scale criteria (eg, laboratory abnormality reported as Grade 4 without manifestation of life-threatening status), it will be left to the Investigator's judgment to also report these abnormalities as serious adverse events. For any adverse event that applies to this situation, comprehensive documentation of the event's severity must be recorded in the subject medical records.

Serious Adverse Events After the Protocol-Required Reporting Period

After EOS, there is no requirement to actively monitor study subjects after the study has ended with regards to study subjects treated by the Investigator. However, if the Investigator becomes aware of serious adverse events suspected to be related to investigational product, then these serious adverse events will be reported to the Sponsor within 24 hours following the Investigator's awareness of the event.

Serious adverse events reported outside of the protocol-required reporting period will be captured within the Sponsor's safety database as clinical trial cases and handled accordingly based on the relationship to investigational product.

If further safety-related data are needed to fulfill any regulatory reporting requirements for a reportable event, then additional information may need to be collected from the subject's records after the subject ends the study.

Method of Detecting Adverse Events and Serious Adverse Events

18 May 2022 Page 32 of 69

Care will be taken not to introduce bias when detecting adverse events and/or serious adverse events. Open-ended and non-leading verbal questioning of the subject is the preferred method to inquire about adverse event occurrence.

Follow-up of Adverse Events and Serious Adverse Events

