Appendix 8: Schedule of Assessments

18 May 2022 Page 67 of 69

	Screening	Check- in	Sotora	sib (Day 1	l) and On Alone	neprazole (Day	y 4-8)		rasib in Comb	oination with
Study Procedures	Days -28 to -2	Day -1	Day 1	Day 2	Day 3	Days 4 to 7	Day 8	Day 9	Day 10	Day 11 (EOS/ET)
Confined to the CRU		X	X	X	X	X	X	X	X	X
Outpatient Visit	X									
Inclusion/Exclusion Criteria	X	X								
Informed Consent	X									
Demographics	X									
Serology	X									
Medical History	X	Xa								
Height and BMI	X									
Weight	X	X								X^b
Drug Screen	X	X								
Alcohol Test		X								
Pregnancy Test (females only) ^c	X	X								X ^b
FSH (postmenopausal females only)	X									
12-lead Electrocardiogram ^d	X	X	X					X		X^b
Vital Signs ^e	X	X	X	X	X			X	X	X^{b}
Clinical Laboratory Evaluations ^f	X	X					X			X^{b}
eGFR ^g	X	X								
Thyroid-stimulating Hormone	X	X								X
Physical Examinationh	X	X								X^b
Sotorasib Dosei			X					X		
Omeprazole Dose ^j						X	X	X		
Sotorasib PK Blood Samples ^k			X	X	X			X	X	X
Adverse Event Monitoring ¹							X			
Serious Adverse Event Monitoring ¹	X					X				
Prior/Concomitant Medications ^m	X					X				

18 May 2022 Page 68 of 69

CONFIDENTIAL AMG 510 20220024

Abbreviations: BMI = body mass index; CRU = Clinical Research Unit; eGFR = estimated glomerular filtration rate; EOS = end of study; AT = early termination; FSH = follicle-stimulating hormone; PK = pharmacokinetic.

- ^a Interim medical history only.
- ^b Assessment to be performed at the EOS or ET.
- ^c Performed in serum at Screening and in urine at all other times. A positive urine pregnancy test will be confirmed with a serum pregnancy test.
- d Electrocardiograms (ECGs) will be collected after the subject has rested in the supine position for at least 5 minutes, and will be obtained prior to the scheduled blood draws. ECGs will be assessed at Screening, Check-in, at predose on Days 1 and 9, and at 0.5, 2, and 4 hours following sotorasib administration; and at EOS or ET. Triplicate ECGs will only be collected at Screening and Check-in if needed to verify eligibility criteria. The 30-minute postdose ECG measurement will have a collection window of \pm 5 minutes, the 2-hour postdose ECG measurement will have a collection window of \pm 10 minutes.

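### The study-wide dosing pause is triggered by one Grade 3 event; read literally, one event first seen at Grade 4 or 5 does not trigger it

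*Protocol*

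**What the plan says.** Protocol Section 4.5 sets two safety rules.

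- **Subject level.** A subject is withdrawn from dosing on, among other criteria, any CTCAE v5.0 "Grade ≥3 adverse event".
- **Study level.** Dosing is paused, and the Investigator and Sponsor review the data, if either of two conditions is met. The first is 2 or more subjects withdrawn for adverse events at least possibly related to sotorasib. The second reads "or if there is 1 Grade 3 event, dosing". It carries no relatedness condition.

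Other provisions bear on the same situation:

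- Section 4.5: "If a subject is withdrawn from dosing, the Sponsor (or designee) will be notified". No time limit is given.
- Section 4.6: "The Sponsor may stop the study or study site participation in the study for medical, safety, regulatory, administrative, or other reasons".
- Section 7.2.1: "All serious adverse events will be collected, recorded, and reported to the Sponsor within 24 hours of the Investigator's awareness of the event". For a Grade 4 finding such as a laboratory abnormality without life-threatening manifestation, "it will be left to the Investigator's judgment to also report these abnormalities as serious adverse events".
- Appendix 8: after Check-in, the row "Clinical Laboratory Evaluations" is marked only on Day 8 and Day 11.

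**The concern.** The two rules stand a few lines apart and use different grade thresholds. The withdrawal rule has the ≥ sign and the pause rule does not. On the literal text the response is inverted: one Grade 3 event stops dosing for everyone, while one event first seen at Grade 4 or 5 stops it only for the subject affected.

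A pause rule exists so that other subjects are not dosed before a severe event has been reviewed. Here the dose at stake is the second 960 mg sotorasib dose on Day 9. The rule should cover the most severe events in its own words, without relying on the site to infer them.

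**Working it through.** The plan states no figure to reproduce, so the check is a reading of the rules plus simple counting.

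**1. Apply Section 4.5 to one event in one subject, with no earlier sotorasib-related withdrawal.**

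| Grade when first observed | Subject withdrawn (≥3)? | Two or more related withdrawals? | Literal Grade 3 event? | Automatic study pause? |
|---|---|---|---|---|
| 3 | Yes | No (1 at most) | Yes | Yes |
| 4 or 5 | Yes | No (1 at most) | No | No |

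An event seen at Grade 3 that later worsens has already met the trigger. The gap is therefore confined to events first observed at Grade 4 or 5.

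**2. Look for another automatic pause.** Section 4.6 gives the Sponsor discretion. Section 7.2.1 requires a report of serious events, not a pause. Appendix 7 governs withholding and discontinuation in the individual subject. The SAP has no stopping rule. None closes the gap.

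**3. Can an event first appear at Grade 4?**

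- *Laboratory findings.* Appendix 8 schedules clinical laboratory draws at Screening, Day -1, Day 8 and Day 11. That is 4 draws, which agrees with the maximum of 4 in Appendix 3. From the Day 1 dose to the next scheduled draw is 8 − 1 = 7 days, so an asymptomatic change could pass Grade 3 unseen. From the Day 8 draw to the second sotorasib dose is 9 − 8 = 1 day.
- *Clinical events.* Section 1.4.1.2 describes interstitial lung disease/pneumonitis in treated patients as Grade 3 or 4 at onset. Those patients had prior immunotherapy or radiotherapy, so the risk here is lower, and such events would also be reported as serious.

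**4. How many other subjects could still be due the Day 9 dose?** Section 3.1 states: "Up to 14 subjects will be enrolled to ensure that 12 subjects complete the study".

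- With 14 subjects: at most 14 − 1 = 13, at least 0.
- With 12 subjects: at most 12 − 1 = 11, at least 0.

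The upper end assumes that all subjects share one dosing calendar and that the event is known before Day 9 dosing. The lower end assumes that all the others have already had that dose.

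**The case against.** The strongest reply is that the literal reading is selective. In a trigger of this kind the count of 1 is plainly a minimum, so the 3 should be read as a minimum too, especially beside a withdrawal rule set at Grade 3 or above. As a statement of intent this stands. But the two numbers do not behave alike. Events normally come to light one at a time, so reading the count exactly changes little in practice, because the first event already triggers the pause. Reading the grade exactly does matter when an event is first seen above 3.

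Second, the uncovered case is narrow. Fatal and life-threatening events are serious by definition and reach the Sponsor within 24 hours, as do the combined transaminase and bilirubin or INR elevations defined in Appendix 7. Every Grade 3 or higher event also withdraws the subject and leads to notice to the Sponsor. All of this is correct and limits the severity. None of it is an automatic pause.

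Third, under Section 7.2.2 and Appendix 1 a laboratory abnormality generally has to be judged clinically significant before it counts as an adverse event, so the amended trigger would still rest partly on the Investigator's judgment. That is true, but the step comes before either wording and applies equally at Grade 3. The fix governs what happens once the finding is an adverse event.

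Fourth, the documents give no laboratory turnaround time. If the Day 8 results arrive after the Day 9 dose, neither wording protects that subject group on that day. This stands as a limit on the laboratory example. It does not affect the reading of the rule.

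**Conclusion.** The concern holds. As written, Section 4.5 gives no automatic study-wide pause for a single event first observed at Grade 4 or 5, and nothing elsewhere in the protocol or SAP provides one.

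It is a minor wording defect. The probability of such an event is low (the documents allow no estimate), the intended meaning is hardly in doubt, and the Sponsor has discretionary means to act. The exposure range has little precision without a dosing calendar. The primary pharmacokinetic comparison is not touched. Because the rule has no relatedness condition, it already applies whatever the cause, and that feature needs no change.

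**What to change.** In Protocol Section 4.5, insert ≥ before the 3 in the single-event trigger, so that one event of Grade ≥3 pauses dosing and the threshold matches the withdrawal rule. Leave the rest of the sentence as it is.

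The cost is one symbol in a protocol amendment, which under Appendix 6 needs IRB approval, so it can sensibly be combined with any other pending change. Sample size, schedule and analysis are unaffected.
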